1.0 Objectives

1.1 Study Objectives

Describe the purpose, specific aims or objectives. State the hypotheses to be tested.

The purpose of this study is to examine the feasibility of using sip^{IT} tools (i.e., wrist-worn sensors, smart water bottles, mobile applications) to increase compliance with physician-recommended fluid consumption guidelines in participants with a history of urolithiasis. The study aims to: 1) deliver notifications regarding fluid consumption to the FitBit Versa and the participant's smartphone based on the participant's assessed fluid intake, and 2) determine the acceptability of using the sip^{IT} tools to increase fluid consumption. It is hypothesized that receiving notifications regarding fluid consumption will lead to an increased compliance in attaining fluid consumption guidelines. Further, it is hypothesized that the frequency of notifications will diminish across the study duration.

1.2 Primary Study Endpoints

State the primary endpoints to be measured in the study. Clinical trials typically have a primary objective or endpoint. Additional objectives and endpoints are secondary. The endpoints (or outcomes), determined for each study subject, are the quantitative measurements required by the objectives. Measuring the selected endpoints is the goal of a trial (examples: response rate and survival).

The objective is to determine the acceptability of the sip^{IT} tools for participants with a history of urolithiasis who seek to increase fluid intake as recommended by physician guidelines.

1.3 Secondary Study Endpoints

State the secondary endpoints to be measured in the study.

- 1) Assess the usability of sip^{IT} tools and the burden upon participants.
- 2) Characterize changes in the frequency of fluid intake reminder notifications over three months.

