7.0 Study Design and Procedures

7.1 Study Design

Describe and explain the study design.

Participants will be asked to fill out baseline questionnaires and height and weight will be measured at the beginning of the study. Additional questionnaire completion and interviews will take place at one month and three months. Participants will wear a Fitbit Versa smartwatch and use an H₂OPal water bottle (and install their associated mobile apps on the participant's personal smartphone) to track their fluid consumption over the entire three month study. If one of the measurement tools (i.e., self-monitoring in the H₂OPal app, the H₂OPal water bottle, the sip^{IT} watch app) does not detect a drinking event within 30 minutes, a text message prompting fluid consumption will be sent to the participant's smartphone and smartwatch. If one of the measurement tools detects drinking, no notification will be delivered.

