7.4 Test Article(s) (Study Drug(s) and/or Study Device(s))

7.4.1 Description

Provide a brief description of all test articles (drugs (including any foods and dietary supplements), devices and/or biologics used in the research including the purpose of their use and their approval status with the Food and Drug Administration (FDA). Include information about the form of the drug product (e.g., tablets, capsules, liquid).

The Fitbit Versa worn on the nondominant wrist will be utilized to monitor the drinking motion of the participant and the H2O Pal devices will be utilized to record the amount of water consumed. The custom app developed for our laboratory by West Arete receives the outputs from the water bottle and the Fitbit Versa and determines if a drinking event has occurred within the past 30 minutes. The server log records the time of the drinking event, the heart rate (to assure wear of the device) and the activity data. If a drinking event has occurred within 30 minutes, the participant is not contacted. If no drinking event has occurred within 30 minutes a

reminder notification is delivered to the participant. The server logs the notification and the response from the participant.

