8.2 Sample size determination

If applicable, provide a justification of the sample size outlined in section 8.1 – to include reflections on, or calculations of, the power of the study.

The above sample size is based on resource constraints for a feasibility study. Only descriptive statistics will be calculated; therefore, a power analysis was not conducted.

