8.3 Statistical methods

Describe the statistical methods (or non-statistical methods of analysis) that will be employed.

Descriptive statistics will be employed to assess feasibility of using sip^{IT} tools for increasing fluid consumption guidelines as well as to assess participant acceptability of using the sip^{IT} tools.

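### Does the reminder-frequency endpoint need a defined denominator and analysis set before its trend can be described?

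*Combined protocol and SAP*

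**What the plan says.** Section 1.3 sets the secondary endpoint: "Characterize changes in the frequency of fluid intake reminder notifications over three months". Section 1.1 adds a direction, directly after the hypothesis that reminders will improve compliance with fluid guidelines: "it is hypothesized that the frequency of notifications will diminish across the study duration".

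The statistical plan is short. Section 8.2 says "Only descriptive statistics will be calculated; therefore, a power analysis was not conducted". Section 8.3 begins "Descriptive statistics will be employed to assess feasibility" and goes on to acceptability; it does not name reminder frequency.

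The sending rule is in sections 7.1 and 7.4.1. The app "determines if a drinking event has occurred within the past 30 minutes", and section 7.1 says "If one of the measurement tools detects drinking, no notification will be delivered". Section 7.1 lists three tools: the watch app, the bottle, and self-monitoring in the bottle's app. On the data kept, section 7.4.1 says "The server log records the time of the drinking event, the heart rate (to assure wear of the device) and the activity data". It adds that notifications and responses are logged and that the bottle "devices will be utilized to record the amount of water consumed".

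Three other places bear on the count. Section 3.3.2 lets the researcher withdraw a participant after 7 days of non-wear and replaces those withdrawn. Section 7.4.4 provides daily checks of the database and contact after three days without a response or a heartbeat. Blocked hours are called do-not-disturb times in sections 7.2.1 and 7.2.2 and sleep times in section 7.2.4.

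**The concern.** A descriptive summary still has to say what is divided by what, in whom and over which period. None of this is stated. The same log could give a trend per calendar day or per worn hour, in everyone enrolled or in completers only, and those trends need not agree.

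The trigger is a failure to detect drinking, not a low volume. The count therefore depends on whether the watch is worn, whether the bottle and the self-monitoring entry are used, how many hours are blocked, and who is still in the study. Because the falling-reminders hypothesis sits next to the compliance hypothesis, a reader might take a fall as evidence of more drinking and carry it into the later trial. A definition chosen after the trend has been seen would make that worse.

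**Working it through.** There is no planned figure to reproduce: section 8.2 reports no power analysis, and the documents give no rate of reminders, wear or dropout. Every input below except the 30 participants and the 30-minute interval is an assumption. Drinking is held constant throughout.

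**Inputs.** p = chance of a drink in 30 minutes (0.3 to 0.5); c = share of drinks caught by bottle or self-monitoring (0.3 to 0.7); s = watch sensitivity when worn (0.5 to 0.8); W = share of time worn. Detection by any one tool stops the reminder.

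**1. Wear falls from 0.95 to 0.60 and reminders continue while the watch is off.** With fixed windows, reminders per window = 1 - p[c + W·s·(1 - c)].
- p = 0.3, c = 0.7, s = 0.5: 0.74725 to 0.763, +2.1%.
- p = 0.5, c = 0.3, s = 0.8: 0.584 to 0.682, +16.8%.

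With a rolling 30-minute look-back that restarts after each detected drink or reminder, L = -2·ln(1 - p) drinks per hour, r(x) = x/(exp(0.5x) - 1), and reminders per hour = W·r(L[c + s(1 - c)]) + (1 - W)·r(L·c). The same two corners give +1.0% and +8.0%.

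**2. Wear falls by the same amount but reminders stop while the watch is off.** If wear is unrelated to drinking, the count scales with wear: 0.60/0.95 - 1 = -36.8%. The documents do not say which branch applies, so neither sign nor size is fixed.

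**3. Eligible hours change.** Reminders per day scale with unblocked hours: 16 to 14 hours gives 14/16 - 1 = -12.5%; 16 to 12 gives -25%; 14 to 16 gives +14.3%.

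**4. Who contributes.** Take 30 completers at 14 reminders a day, with k leavers counted only in the early period.
- Leavers at 20 a day: k = 3 gives 14/(480/33) - 1 = -3.75%; k = 9 gives 14/(600/39) - 1 = -9.0%.
- Leavers at 10 a day: k = 3 gives 14/(450/33) - 1 = +2.7%; k = 9 gives 14/(510/39) - 1 = +7.1%.

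This shift arises only if different people are pooled across periods. Within-person change does not have it.

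**5. Would reminders per worn hour be better?** Set W = 1 and let c fall from 0.7 to 0.3.
- Fixed windows: p = 0.3, s = 0.8 gives 0.718 to 0.742, +3.3%; p = 0.5, s = 0.5 gives 0.575 to 0.675, +17.4%.
- Rolling look-back, same corners: +1.5% and +7.8%.

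So the worn-time rate removes the wear effect (2.1% to 16.8% in step 1, fixed windows) but stays exposed to a detector effect of the same order (3.3% to 17.4%).

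**The case for a change.** The strongest case for a change is that calling the analysis descriptive does not excuse the missing definition, and that supplying one costs a few lines in section 8.3. Reminders and heart rate are already logged. If reminders stop when the watch is off, fading wear alone could produce the hypothesised fall, and a worn-time rate would remove that artefact if wear is unrelated to drinking. A real improvement can also be hidden: if the chance that a 30-minute window passes without a detected drink falls from 0.5 to 0.4 while eligible hours rise from 14 to 17.5, the count is 2 × 14 × 0.5 = 14 and then 2 × 17.5 × 0.4 = 14 a day.

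What stands is that unit, periods and analysis set are unstated, and that the raw trend is not a measure of intake. What does not stand is that the plan would therefore give a wrong answer. The endpoint is about reminders, not intake, and no section treats one as the other. Where reminders continue during non-wear, fading wear raises the count and works against the hypothesised fall. Prolonged non-wear is limited by the three-day contact rule in section 7.4.4 and the 7-day withdrawal option in section 3.3.2, though part-day non-wear is not. For intake itself, the bottle's recorded volume is more direct, if incomplete.

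The change from do-not-disturb to sleep times looks like uneven drafting. Section 7.2.1 is the only place where blocked times are set, and it sets them once. The wording of sections 7.2.2 and 7.2.4 should be reconciled as a clerical matter.

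**Conclusion.** The omission is genuine, but it is missing detail of the kind an analyst fills sensibly: reminders per participant-day by month, within-person change among those with data in both periods, the number contributing to each, and wear from heart rate shown alongside. That is ordinary practice for a secondary, descriptive endpoint in a 30-person feasibility study sized by resources, and it fits section 8 as written.

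The possible movement with constant drinking is not trivial: from -36.8% to +16.8% for the wear change considered, -25% to +14.3% for eligible hours, and -9.0% to +7.1% for pooled composition. These figures rest entirely on assumed inputs and show only that the raw trend should not be taken for a change in drinking, which the protocol does not do. A worn-time rate would be a reasonable extra summary, but it trades one detector dependence for another of similar size and is not shown to be a better primary summary. No change to the plan is needed.

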2.0 Background

2.1 Scientific Background and Gaps

Describe the scientific background and gaps in current knowledge.

Complying with fluid consumption guidelines provides a variety of health benefits. Patients with a history of urolithiasis are a segment of the population that can benefit from meeting physician-recommended fluid consumption guidelines. Preliminary studies with this population have revealed patient interest in using various technologies (i.e., wrist-worn sensors, smart water bottles, mobile applications) to increase their fluid consumption but we are not aware of any that combine multiple technologies. Our long-term goal is to examine if just-in-time reminder notifications to drink following periods when patients have not been drinking will increase compliance among those with a history of urolithiasis. To prepare for that study, we seek to evaluate the feasibility and acceptability of the sip^{IT} tools in this study.

2.2 Previous Data

Describe any relevant preliminary data.

This study is part three of a set of studies aimed at determining the feasibility of using technology to increase compliance with fluid consumption guidelines. Preliminary data included 1) a focus group of

participants with a history of urolithiasis and 2) a lab study to examine the feasibility of using wrist-worn sensors to detect non-alcoholic drinking events. Data from the focus group revealed that participants are interested in using a variety of technologies (e.g., wrist-worn sensors, smart water bottles, mobile applications) to assist with increasing fluid consumption. Data from the lab study revealed that using wrist-worn inertial sensors to detect drinking events is feasible. Based on data from the lab study, an algorithm was developed to detect these drinking events and has been implemented in a consumer smartwatch app for just-in-time drinking detection.

2.3 Study Rationale

Provide the scientific rationale for the research.

Certain populations, such as those with a history of urolithiasis, can benefit from complying with fluid consumption guidelines. For those patients, complying with fluid consumption guidelines is often the first line of defense in preventing a recurrence of stone episodes. Focus groups with participants with a history of urolithiasis revealed that there is an interest in using wrist-worn sensors and mobile applications to improve compliance. Further, wrist-worn sensors can be used to detect drinking events. The use of wrist-worn sensors (i.e., FitBit Versa), an H₂OPal connected water bottle and fluid consumption monitoring mobile applications – collectively referred to as the sip^{IT} tools – can be used to engage participants over time and support compliance with physician-recommended fluid consumption guidelines. Participants with a history of urolithiasis present an important population to target with these tools given their unique need for complying with fluid consumption guidelines.

3.0 Inclusion and Exclusion Criteria

Create a numbered list below in sections 3.1 and 3.2 of criteria subjects must meet to be eligible for study enrollment (e.g., age, gender, diagnosis, etc.). Indicate specifically whether you will include any of the following vulnerable populations: (You may not include members of these populations as subjects in your research unless you indicate this in your inclusion criteria.) Review the corresponding checklists to ensure that you have provided the necessary information.

- **Adults unable to consent**
 - Review “CHECKLIST: Cognitively Impaired Adults (HRP-417)” to ensure that you have provided sufficient information. HRP-417 can be accessed by clicking the Library link in CATS IRB (<http://irb.psu.edu>).
- **Individuals who are not yet adults (infants, children, teenagers)**
 - If the research involves persons who have not attained the legal age for consent to treatments or procedures involved in the research (“children”), review the “CHECKLIST: Children (HRP-416)” to ensure that you have provided sufficient information. HRP-416 can be accessed by clicking the Library link in CATS IRB (<http://irb.psu.edu>).
- **Pregnant women**
 - Review “CHECKLIST: Pregnant Women (HRP-412)” to ensure that you have provided sufficient information. HRP-412 can be accessed by clicking the Library link in CATS IRB (<http://irb.psu.edu>).
- **Prisoners**
 - Review “CHECKLIST: Prisoners (HRP-415)” to ensure that you have provided sufficient information. HRP-415 can be accessed by clicking the Library link in CATS IRB (<http://irb.psu.edu>).
- **Neonates of uncertain viability or non-viable neonates**
 - Review “CHECKLIST: Neonates (HRP-413)” or “CHECKLIST: Neonates of Uncertain Viability (HRP-414)” to ensure that you have provide sufficient information. HRP-413 and HRP-414 can be accessed by clicking the Library link in CATS IRB (<http://irb.psu.edu>).

3.1 Inclusion Criteria

List the criteria that define who will be included in your study.

- (a) Age 18 years or older
- (b) Fluent in spoken and written English, and capable of providing informed consent
- (c) Own an iPhone (version 6 or higher)
- (d) History of urolithiasis, and
- (e) Willingness to complete all study procedures: completing questionnaires, participating in semi-structured interviews, tracking fluid consumption, wearing a FitBit Versa and receiving notifications on the FitBit and their smartphone for a three-month period

3.2 Exclusion Criteria

List the criteria that define who will be excluded in your study.

- (a) Any medical condition that interferes with regular fluid consumption

3.3 Early Withdrawal of Subjects

3.3.1 Criteria for removal from study

Insert subject withdrawal criteria (e.g., safety reasons, failure of subject to adhere to protocol requirements, subject consent withdrawal, disease progression, etc.).

Participants may withdraw their consent for participating at any time to remove themselves from the study. Participants may also be removed from the study for failure to adhere to protocol requirements.

3.3.2 Follow-up for withdrawn subjects

Describe when and how to withdraw subjects from the study; the type and timing of the data to be collected for withdrawal of subjects; whether and how subjects are to be replaced; the follow-up for subjects withdrawn from investigational treatment.

The researcher can withdraw a participant if they fail to wear the study-provided smartwatch for a period of 7 days. Non-wear will be determined by monitoring heart rate data from the smartwatch. Participants who are withdrawn will be replaced.

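### People withdrawn for not wearing the watch are replaced, but the plan states no exit rating and no denominator, although the watch is part of what the primary acceptability endpoint judges

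*Combined protocol and SAP*

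**What the plan says.** Section 1.2 sets the primary endpoint: "The objective is to determine the acceptability of the" sipIT tools. Sections 1.1 and 2.3 count the wrist-worn sensor (the Fitbit Versa) among those tools. Section 1.3 adds usability "and the burden upon participants", and a second aim: "Characterize changes in the frequency of fluid intake reminder notifications over three months".

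On withdrawal, section 3.3.2 states: "The researcher can withdraw a participant if they fail to wear the study-provided smartwatch for a period of 7 days". It adds: "Non-wear will be determined by monitoring heart rate data from the smartwatch". Then: "Participants who are withdrawn will be replaced". That last sentence covers everyone withdrawn, not only non-wearers. Section 3.3.1 gives two other routes out: non-adherence to the protocol, and the participant's own choice ("Participants may withdraw their consent for participating at any time to remove themselves from the study").

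The template prompt in 3.3.2 asks for "the type and timing of the data to be collected for withdrawal of subjects". The answer below it gives neither.

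After baseline, questionnaires and interviews are placed only at one month and three months (7.1, 7.2.3, 7.2.5). Section 8.1 gives 30 as the number to be enrolled, and 16.2 gives 30 as the number to be recruited. Section 8.3 plans descriptive statistics and names no analysis set, denominator or treatment of withdrawn participants.

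**The concern.** Sustained non-use of the watch may be a sign that the participant does not accept it. Under 3.3.2 it can also lead to removal from the study and to the place being refilled. If those removed are never asked for a rating, and the report describes those who remain, the summary is selected towards people who tolerate the watch. Usability and burden would be affected in the same way.

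The notification series has a related problem. The people contributing to it change over the three months. An unworn watch also detects no drinking, so non-wear can itself raise the number of reminders sent.

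The descriptive summary is the study's whole quantitative product (8.2), and 2.1 says it prepares a later study. Ratings not collected at exit cannot be recovered afterwards.

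**Working it through.** **The plan's own figure.** Section 8.2 bases the 30 on resources, with no power analysis, so there is no sample-size formula to reproduce. The one calculation attached to it, in 16.2, does reproduce: 433,563 / 11 = 39,415, and 30 / 39,415 = 0.076%, against a stated value of about 0.075%.

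**Who is left without a rating.** A 7-day non-wear withdrawal can occur from about day 7, and the first follow-up rating comes at one month.
- Withdrawn before the one-month visit: no post-baseline rating.
- Withdrawn between the two visits: a month-1 rating but no month-3 rating.

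**Whether other data fill the gap.** The server logs drinking events, heart rate, activity, notifications and responses (7.4.1). Staff contact anyone with three days of no response or no heartbeat (7.4.4), to check for safety or study issues and willingness to continue. Neither is described as an acceptability assessment.

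**Size, in general form.** The documents give no withdrawal or acceptability rate, so the inputs below are assumptions. Let k people be withdrawn, replaced and unrated, let 30 remain and all be rated, let R be the mean rating (or proportion accepting) among those who remain, and W the same among those withdrawn.

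Mean over everyone given devices = (30R + kW) / (30 + k)

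Overstatement = R − that mean = [k / (30 + k)] × (R − W)

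| Assumed k | 30 excludes those withdrawn: k/(30+k) | 30 includes them: k/30 |
|---|---|---|
| 1 | 1/31 = 3.2% | 1/30 = 3.3% |
| 3 | 3/33 = 9.1% | 3/30 = 10.0% |
| 6 | 6/36 = 16.7% | 6/30 = 20.0% |

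The overstatement is zero if k = 0 or R = W, and negative if those withdrawn would rate the tools higher. The last column applies if enrolment stops at 30 in total, leaving 30 − k who remain.

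**Effect of existing month-1 ratings.** The weights above suit a month-3 summary. For a summary of any post-baseline rating that keeps those withdrawn after month 1, only the m people withdrawn before month 1 are unrated, and their weight is m/(30 + k). With assumed k = 6 and m = 3 it is 3/36 = 8.3%, half of 16.7%.

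**One illustration.** Assume a yes/no rating, 26 of 30 accepting (86.7%) among those who remain, and 6 withdrawn and unrated. Over all 36 the proportion lies between 26/36 = 72.2% (none of the six accept) and 32/36 = 88.9% (all six accept). With five accepting it is 31/36 = 86.1%. So 86.7% is too high if five or fewer of the six would accept, and too low if all six would. Assuming 24 of 30 (80.0%) instead gives 24/36 = 66.7% to 30/36 = 83.3%. The width is 6/36 = 16.7 points in both cases.

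**The number 30.** With k replacements, total enrolment is 30 + k if 30 people are to remain. Enrolling 30 and replacing those withdrawn therefore agree only if k = 0 or if the 30 means something other than total enrolment.

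**The case against.** The strongest reply is that the consequence is modest and unproven. The study is descriptive, with no test, threshold or go/no-go rule. Harm requires that somebody is withdrawn, that those withdrawn are left out of the summary, and that they would have rated the tools lower. The documents establish none of the three, and withdrawal for non-wear is discretionary. This stands as a limit on the claim. A reader might infer that the report will cover only those who remain and will therefore be biased upward. Nothing in the documents says so, and nothing rules it out.

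Other objections stand in part:
- **Non-wear is not the same as rejection.** It is inferred from heart rate data, so a lost signal or an illness could look the same. This is a reason to record why people leave.
- **Not everyone withdrawn is unrated.** Those who leave after month 1 already have one set of ratings.
- **The 30 has a literal meaning.** Sections 8.1 and 16.2 speak of enrolling and recruiting, so it would go too far to call the number undefined. What is missing is how it fits with replacement. The 8.1 prompt asks, where applicable, for the number enrolled to be separated from the number needed to complete, and a replacement rule makes that applicable.
- **Unseen material.** Section 20.1.1 refers to an operating procedure manual, which is not part of these documents and might contain an exit form. The claim is limited to what this document states.
- **One analysis set for every endpoint would not work.** An unrated person cannot contribute to a mean score, and adding non-worn days to notification counts could distort them. The remedy has to be set endpoint by endpoint.

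**Conclusion.** The point holds as a gap in the stated plan that should be fixed. Following 3.3.2 as written leaves anyone withdrawn before month 1 without an acceptability rating and refills the place. The plan gives no exit assessment and no denominator, and does not reconcile enrolling 30 with replacing those withdrawn. Confidence is high for these omissions.

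The direction of any bias is conditional: acceptability is overstated if the summary is restricted to those who remain and those withdrawn would have rated the tools lower. The size is not derivable from the documents. The weights of 3.2% to 16.7% (or 3.3% to 20.0%) rest on assumed withdrawals of 1 to 6, on all of them being unrated, and on everyone who remains being rated. They shrink where month-1 ratings are used. The documents do not support calling the acceptability result invalid, or treating every case of non-wear as non-acceptance.

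**What to change.** 1. **Section 3.3.2.** Offer each participant withdrawn by the researcher one exit completion of the existing follow-up questionnaires and interview, remotely if needed. Offer it to those who withdraw consent only if they agree to give further data. Record the reason for every withdrawal, with device or sync failure and illness shown separately.
2. **Section 8.3.** Report the number, timing and reasons for withdrawal among all participants given the devices, as a feasibility and acceptability result.
   - *Acceptability and usability:* use all participants given the devices as the denominator. For a proportion, show the none-accept and all-accept bounds for the unrated. For a score, report it with the number unrated.
   - *Notification frequency:* summarise it separately, distinguishing worn from non-worn days with the heart rate data already logged.
3. **Section 8.1.** Say whether the 30 includes replacements, and align 16.2.

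The withdrawal and replacement rules may stay as they are. The cost is amendment wording and a few exit contacts. The existing follow-up visits last 1 and 1.5 hours, some people who have stopped wearing the watch may decline, and section 14.0 does not cover payment for an exit contact, so that should be settled in the same amendment. The reported acceptability figure may be less favourable.
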